### **9.6.3 Reporting Serious Adverse Events**

All SAEs must be reported by the investigational staff within 24 hours of learning about the event using the SAE Report form to the Sponsor or its designee (eg, CRO Pharmacovigilance group). Refer to the Study Reference Manual for contact information for reporting SAEs.

The initial report should be promptly followed by detailed, written reports, which will include copies of relevant hospital case reports, autopsy reports, and other documents when requested and applicable.

For a follow-up report to the authorities, the monitor may be required to collect further information for a final evaluation of the case. Reporting to the respective country Health Authorities will be the responsibility of the Sponsor and the CRO.

The CRO will be responsible for informing all central Institutional Review Boards (IRBs)/Independent Ethics Committees (IECs) of SAEs as required. It will be the responsibility of the individual Investigators to inform any local IRBs/IECs of SAEs as required. Correspondence with the IRB(s)/IEC(s) relating to the reporting of SAEs will be retained in the study file.

### **9.7 Clinical Laboratory Abnormalities and Other Abnormal Assessments as AEs or SAEs**

Laboratory abnormalities are usually not recorded as AEs or SAEs. Clinical laboratory abnormalities that require medical or surgical intervention or lead to study drug interruption or discontinuation must be recorded as an AE or SAE, if applicable. The modified DAIDS Table for Grading the Severity of Adult and Pediatric AEs ([Appendix 1](#)) will be used to assess the severity of clinical laboratory abnormalities. In addition, clinical laboratory or other abnormal assessments (eg, ECG and vital signs) that are associated with signs and/or symptoms must be recorded as an AE or SAE if they meet the definition of an AE or SAE described in [Sections 9.1](#) and [9.6](#). If the clinical laboratory abnormality or abnormal assessment is part of a syndrome or diagnosis, record the syndrome or diagnosis (eg, anemia), not the clinical laboratory result (ie, decreased hemoglobin).

### **9.8 Overdose**

An overdose is defined as the accidental or intentional administration of any dose of a product which is above the maximum recommended dose as per protocol or in the product labelling (as it applies to the daily dose of the subject in question). The Medical Monitor may be contacted for questions concerning potential cases of overdose. An overdose is not in and of itself considered to be an AE unless it results in untoward medical effects. Any AE associated with an overdose or incorrect administration of study drug should be entered in the subject's source documentation and Adverse Event eCRF. If the associated AE fulfills the criteria of an SAE, then the event should be reported to the Sponsor or CRO within 24 hours after the site learns of the event.

## **9.9 Pregnancy**

### **9.9.1 Female Subjects Who Become Pregnant**

The Investigator will collect pregnancy information on any female subject who becomes pregnant while participating in this study. The initial information will be recorded on the Pregnancy Reporting form and submitted to the Sponsor or its designee within 24 hours of learning of a subject's pregnancy. Refer to the Study Reference Manual for contact information for reporting a pregnancy.

The subject will be followed to determine the outcome of the pregnancy. The Investigator will collect follow-up information on the subject and the neonate and the information will be forwarded to the Sponsor or its designee. Generally, follow-up will not be required for longer than 6 to 8 weeks beyond the estimated delivery date. Any termination of pregnancy will be reported, regardless of fetal status (presence or absence of anomalies) or indication for the procedure.

While pregnancy itself is not considered to be an AE or SAE, any pregnancy complication or elective termination of a pregnancy for medical reasons will be reported as an AE or SAE. A spontaneous abortion (occurring at <22 weeks gestational age) or still birth (occurring at >22 weeks gestational age) is always considered to be an SAE and will be reported as such.

Any female subject who becomes pregnant while participating in the study will discontinue the study drug immediately.

### **9.9.2 Male Subjects With Partners Who Become Pregnant**

The Investigator will attempt to collect pregnancy information on any male subject's female partner who becomes pregnant while the male subject is participating in this study.

After obtaining the necessary signed informed consent from the pregnant female partner directly, the Investigator will record pregnancy information on the Pregnancy Reporting form and submit it to the Sponsor or its designee within 24 hours of learning of the partner's pregnancy. The female partner will also be followed to determine the outcome of the pregnancy. Information on the status of the mother and child will be forwarded to the Sponsor. Generally, the follow-up will be no longer than 6 to 8 weeks following the estimated delivery date. Any termination of the pregnancy will be reported regardless of fetal status (presence or absence of anomalies) or indication for the procedure. Refer to the Study Reference Manual for contact information for reporting a pregnancy.

## **9.10 Toxicity Management**

Administration of study drug may be interrupted or discontinued due to a clinical event or laboratory abnormality. The Medical Monitor should be consulted prior to dose interruption or discontinuation of study drug unless the Investigator believes that immediate action is warranted to ensure the continued safety of subject.

Grade 3 and 4 clinically significant laboratory abnormalities should be confirmed by repeat testing within 3 days of receipt of results and before study drug interruption or discontinuation, unless such a delay is not consistent with good medical practice.

Any questions regarding toxicity management should be directed to the Medical Monitor.

#### **9.10.1 Grades 1 and 2 Clinical Event or Laboratory Abnormality**

- Continue study drug at the discretion of the Investigator.

#### **9.10.2 Grade 3 Clinical Event or Laboratory Abnormality**

- For Grade 3 clinical event or clinically significant laboratory abnormality, the study drug may be continued if considered to be unrelated to investigational medicinal product.
- For a Grade 3 clinical event or clinically significant laboratory abnormality confirmed by repeat testing, that is considered to be related to the study drug, the study drug should be withheld until the toxicity returns to  $\leq$ Grade 2.
- If a laboratory abnormality recurs to  $\geq$ Grade 3 following rechallenge with the study drug and is considered related to the study drug, then the study drug should be permanently discontinued and the subject managed according to local practice. Recurrence of laboratory abnormalities considered unrelated to the study drug may not require permanent discontinuation.

#### **9.10.3 Grade 4 Clinical Event or Laboratory Abnormality**

- For a Grade 4 clinical event or clinically significant Grade 4 laboratory abnormality confirmed by repeat testing that is considered related to the study drug, the study drug should be permanently discontinued and the subject managed according to local practice. The subject should be followed as clinically indicated until the laboratory abnormality returns to Baseline or is otherwise explained, whichever occurs first. A clinically significant Grade 4 laboratory abnormality that is not confirmed by repeat testing should be managed according to the algorithm for the new toxicity grade.
- The study drug may be continued without dose interruption for a clinically nonsignificant Grade 4 laboratory abnormality (eg, Grade 4 creatine kinase after strenuous exercise, or triglyceride elevation that is nonfasting or that can be medically managed) or a clinical event considered unrelated to the study drug.

#### **9.10.4 Management of Alanine Aminotransferase (ALT) Elevations**

All subjects participating in the study will be closely monitored for ALT elevations and/or signs of potential decline in hepatic function (see [Figure 7](#)). Subjects experiencing ALT elevations  $\geq 2\times$  Baseline (Day 1) or on-treatment nadir and  $>2\times$  ULN during study treatment or during post-treatment follow-up should be closely monitored with regular Unscheduled Visits every 1 to 2

weeks at the discretion of the Investigator. At these visits, the following laboratory tests will be performed: ALT, AST, total bilirubin (if total bilirubin is elevated, reflex to direct bilirubin), serum albumin, INR and creatine kinase. The Investigator will determine if other Unscheduled Visit assessments should be performed. Additionally, the following guidance is provided for management of subjects with ALT elevations:

- ALT Elevation Without Declining Hepatic Function
  - All subjects with an ALT elevation on treatment, defined as ALT  $>2\times$  Baseline or on treatment nadir and  $\geq 10\times$  ULN, should have the ALT findings confirmed within 3 days of receipt of the original results. All subjects should return for an Unscheduled Visit.
  - If the ALT elevation is confirmed, then an additional Unscheduled Visit will be performed to further evaluate the subject. At this visit, the following laboratory tests will be performed: ALT, AST, total bilirubin (if total bilirubin is elevated, reflex to direct bilirubin), serum albumin, INR, creatine kinase, HBV DNA, quantitative HBV serologies (HBeAg [reflex qualitative HBeAg if quantitative HBeAg is negative] and HBsAg [reflex qualitative HBsAg if quantitative HBsAg is negative]), HAV immunoglobulin M (IgM), HCV RNA, HDV RNA, HEV IgM, ANA, smooth muscle antibodies and anti-LKM1 antibodies, EBV DNA, CMV DNA, HSV DNA, and total IgG. The Investigator will determine if other Unscheduled Visit assessments should be performed.
    - If an intercurrent illness is determined to be causal, subjects with an ALT elevation without declining hepatic function and without contraindications may continue treatment and the intercurrent illness should be treated as deemed medically appropriate by the Investigator.
    - Subjects with an ALT elevation without declining hepatic function and without contraindications may continue treatment with study drug under close observation.
    - If ALT is rising at the confirmatory visit, subjects should return for an Unscheduled Visit every 2 to 5 days until the ALT elevation has stabilized. At these visits, the following laboratory tests will be performed: ALT, AST, total bilirubin (if total bilirubin is elevated, reflex to direct bilirubin), serum albumin, INR, creatine kinase, HBV DNA, quantitative HBV serologies (HBeAg [reflex qualitative HBeAg if quantitative HBeAg is negative] and HBsAg [reflex qualitative HBsAg if quantitative HBsAg is negative]). The Investigator will determine if other assessments specified in [Section 8.4](#) should be performed. Subjects whose ALT has stabilized should continue to be monitored weekly (or more frequently, as deemed necessary by the Investigator) until ALT values return to normal or Baseline levels.
    - Subjects with an ALT elevation without declining hepatic function and without contraindications should discontinue study drug if the ALT remains persistently elevated for  $>4$  weeks
- ALT Elevation With Declining Hepatic Function

[figure not shown]
- Subjects with confirmed ALT elevation with biochemical evidence of declining hepatic function should be discontinued from study treatment. This is defined as:
  - ALT elevation  $\geq 2 \times$  Baseline or nadir and  $> 2 \times$  ULN AND
    - Direct bilirubin increase to  $\geq 2 \times$  Baseline and  $\geq 2 \times$  ULN OR
    - Albumin decline  $\geq 0.5$  g/dL OR INR  $> 1.5 \times$  Baseline OR
    - Symptoms of liver inflammation (eg, fatigue, weakness, lack of appetite, nausea, vomiting, jaundice, or discolored feces)
- Subjects with evidence of declining hepatic function should return for an Unscheduled Visit every 2 to 5 days until the relevant laboratory values stabilize. Subjects whose hepatic function has stabilized should continue to be monitored weekly (or more frequently as deemed necessary by the Investigator) until the relevant laboratory values return to normal or Baseline.

All subjects with ALT elevation without or with declining hepatic function should continue to be followed on their regular study visit schedule, with the addition of unscheduled visits as described above. If the posttreatment ALT elevation has not substantially resolved by the last study follow-up visit, subjects should continue to return to clinic as deemed medically appropriate by the Investigator, in consultation with the Sponsor until the ALT elevation is documented to be either resolved or resolving (defined as consistent ALT declines of 10% or more or normalization of ALT) on at least 2 successive visits.

Following cessation of study drug treatment under this protocol, all subjects will be closely followed for ALT elevations and/or signs of potential decline in hepatic function. This applies to all subjects whether they prematurely discontinue study drug or complete the study treatment per protocol. Any subject with a post-treatment ALT elevation without evidence of declining hepatic function or a post-treatment ALT elevation with evidence of declining hepatic function as defined above, will be evaluated as noted above.

If 5 or more subjects meet these flare management criteria, the relevant regulatory agencies will be notified, and subsequent steps will be determined after consultation with these agencies.

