#### 4.1.2 NrtI-Restart Criteria

Subjects who meet the Treatment Stopping Criteria at the Week 48 assessment but subsequently meet **ANY** of the below NrtI-Restart Criteria, will restart treatment with NrtI and remain in follow-up through Week 96.

NrtI-Restart Criteria are:

- ALT > 10 ×ULN, confirmed by repeat
- ALT > Baseline and > ULN, confirmed by repeat, and
  - Direct bilirubin > 2.0 × ULN, confirmed by repeat, or
  - International Normalized Ratio > 1.5, confirmed by repeat
- ALT ≥ 2 – 5 × ULN AND HBV DNA > 2000 IU/mL for 12 weeks
- ALT elevations ≥ 5 – 10 ×ULN AND HBV DNA > 2000 IU/mL for 4 weeks
- Any clinical decompensation, regardless of HBV DNA level
- Investigator discretion

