**Table 12. Clinical Laboratory Tests**

Panel	Tests
Chemistry	Glucose, sodium, potassium, chloride, bicarbonate, calcium, blood urea nitrogen, creatinine, creatine kinase, uric acid, total and direct bilirubin, ALT, AST, GGT, alkaline phosphatase, LDH, triglycerides, total cholesterol, phosphorous (inorganic), total protein, albumin, amylase, lipase
Hematology	Hemoglobin, hematocrit, red blood cell count, RBC indices (MCV), reticulocyte count, white blood cell count including, lymphocytes (total and differential), monocytes, neutrophils, eosinophils, basophils, platelet counts
ALT Elevation Management (Section 9.10.4)	ALT, AST, total bilirubin, serum albumin, creatine kinase, INR, HBV DNA, quantitative HBV serologies (HBeAg [reflex qualitative HBeAg if quantitative HBeAg is negative] and HBsAg [reflex qualitative HBsAg if quantitative HBsAg is negative]), HAV immunoglobulin M (IgM), HCV RNA, HDV RNA, HEV IgM, ANA, smooth muscle antibodies and anti-LKM1 antibodies, EBV DNA, CMV DNA, HSV DNA, and total IgG.
Coagulation	Prothrombin time/INR and aPTT
Urinalysis	pH, specific gravity, protein, glucose, ketones, and occult blood
FibroTest	alpha-2-macroglobulin, haptoglobin, apolipoprotein A1, GGT, total Bilirubin, ALT
APRI	AST, platelet count
Other	AFP, HbA1c, creatinine clearance calculated by Cockcroft-Gault (Cockcroft 1976)
Pregnancy Tests	For females of child-bearing potential only; a serum pregnancy test must be performed at Screening, and both serum and urine are required at Day 1; a urine pregnancy test must be performed at all subsequent visits, if positive, confirm with a serum pregnancy test
Urine Drug Test	Amphetamine/methamphetamine, barbiturates, benzodiazepines, cocaine metabolite, ethanol, opiates, phencyclidine, and propoxyphene
Serology a	HAV, HCV, HDV, HEV, and HIV
Virology	HBV DNA, HBV RNA, HBsAg b , HBeAg, HBcrAg, HBsAb and HBeAb, HBV resistance monitoring

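### The ALT-flare test lists make direct bilirubin conditional on an elevated total, yet two safety rules turn on direct bilirubin itself: sites have conflicting instructions, and that limb could be evaluated late

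*Combined protocol and SAP*

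**What the plan says.** **Flare test lists (protocol 9.10.4).** A subject whose ALT is at least twice Baseline or on-treatment nadir, and above 2×ULN, is seen every 1 to 2 weeks, whether on treatment or in follow-up. After ALT and AST, those visits measure "total bilirubin (if total bilirubin is elevated, reflex to direct bilirubin), serum albumin, INR and creatine kinase". Two further lists carry the same reflex condition: one for a confirmed elevation of at least 10×ULN, the other for visits every 2 to 5 days while ALT is rising. The ALT Elevation Management row of Table 12 begins "ALT, AST, total bilirubin, serum albumin, creatine kinase, INR, HBV DNA, quantitative HBV serologies" and names neither direct bilirubin nor a reflex. The Chemistry row of the same table includes both total and direct.

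**Rules that use direct bilirubin.** The definition of declining hepatic function (9.10.4) has a limb reading "Direct bilirubin increase to" at least twice Baseline and at least twice ULN. The restart rule (4.1.2), for a subject whose ALT is above both Baseline and ULN, has the limb "Direct bilirubin > 2.0 × ULN, confirmed by repeat, or" followed by an INR alternative. Neither limb mentions total bilirubin.

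**What is drawn at an unscheduled visit.** Table 9 marks chemistry in its Unscheduled Visit column, and footnote b sends subjects with a 9.10.4 ALT elevation to that visit. Section 8.4 takes bloods only where they apply and refers to 9.10.4 for the minimum set in ALT elevations. Tables 10 and 11, which govern follow-up, have no Unscheduled Visit column.

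**The concern.** A limb cannot be met on an analyte that was not measured. A site that follows the 9.10.4 list to the letter, and sees total bilirubin in range, has no direct bilirubin to set against either rule.

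On treatment, the decline rule leads to discontinuation of study treatment. In follow-up, a post-treatment elevation "with evidence of declining hepatic function as defined above, will be evaluated as noted above", and finding decline shortens the visit interval: "Subjects with evidence of declining hepatic function should return for an Unscheduled Visit every 2 to 5 days until the relevant laboratory values stabilize". A direct bilirubin not measured could delay either step.

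For subjects who have stopped all treatment, including NrtI, it could also delay restart. The SAP effect is descriptive only: Section 7.2.3.2 counts subjects meeting the decline criteria, and an unmeasured value cannot be counted.

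**Working it through.** The plan states no figure to reproduce. The check sets the instructions side by side, finds when the limbs can be met without the reflex firing, and measures how long that could last.

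**1. Instructions compared**

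| Source | Direct bilirubin at a flare visit |
|---|---|
| 9.10.4, all three lists | Only if total is elevated |
| Table 12, ALT row | Not named |
| 8.4 | Chemistry where applicable; ALT minimum from 9.10.4 |
| Table 9 Unscheduled Visit column, footnote b, Table 12 Chemistry row | Always |
| Tables 10 and 11 | No unscheduled column; chemistry at every scheduled visit |
| 8.1 | Presents Table 9 as covering all Cohort 1 procedures |

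The conflict is clear on treatment. It is arguably stronger in follow-up, where the tables are silent on unscheduled visits, although footnote b and 8.1 can be read to carry Table 9 there.

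**2. When a limb can be met with total in range**

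9.10.4 does not define elevated; I take it as above ULN. Direct is part of total, so with no reflex, direct ≤ total ≤ total ULN. The restart limb needs direct > 2 × direct ULN. Both hold only if

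2 × direct ULN < total ULN, that is, direct ULN < half of total ULN.

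The ULN part of the decline limb gives the same condition, apart from exact equality, because it uses ≥. The documents give no bilirubin ULNs. Taking total ULN of 1.0 to 1.3 and direct ULN of 0.2 to 0.6 mg/dL as assumptions, the cells show the smallest share of total that must be direct (2 × direct ULN ÷ total ULN):

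| Direct ULN | 2 × direct ULN | Total ULN 1.0 | Total ULN 1.2 | Total ULN 1.3 |
|---|---|---|---|---|
| 0.2 | 0.4 | 40% | 33% | 31% |
| 0.3 | 0.6 | 60% | 50% | 46% |
| 0.4 | 0.8 | 80% | 67% | 62% |
| 0.5 | 1.0 | impossible | 83% | 77% |
| 0.6 | 1.2 | impossible | impossible | 92% |

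These are floors, reached with total exactly at its ULN; a lower total needs a higher share. The decline limb also needs twice Baseline. With Baseline at the screening ceiling of 1.2 × direct ULN (exclusion 11c), that is 2.4 × direct ULN, or 0.48 to 0.96 mg/dL for direct ULN of 0.2 to 0.4, still below every assumed total ULN.

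**3. How long it could last**

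Table 10 chemistries after Week 48 fall at Weeks 50, 52, 54, 56, then every 4 weeks to 96. That is 4 intervals of 2 weeks and 10 of 4 weeks (40 of 48 weeks).

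- Longest follow-up interval: 28 + 5 + 5 = 38 days. On treatment: 28 + 3 + 3 = 34 days.
- Flare visits strictly inside 28 days: 1 if every 14 days (day 14), 3 if every 7 days (days 7, 14, 21). Inside 38 days: 2 and 5.

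**4. Who is exposed for restart**

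| ALT, off treatment | Laboratory restart triggers |
|---|---|
| Above 10×ULN | "ALT > 10 ×ULN, confirmed by repeat" is enough alone |
| 5 to 10×ULN | HBV DNA above 2000 IU/mL for 4 weeks; or direct bilirubin or INR |
| 2 to 5×ULN | "ALT ≥ 2 – 5 × ULN AND HBV DNA > 2000 IU/mL for 12 weeks"; or direct bilirubin or INR |

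The second and third lists follow confirmed ALT of at least 10×ULN, where ALT alone essentially triggers restart. The restart effect is therefore essentially confined to the 1-to-2-weekly list with ALT up to 10×ULN. In that band only direct bilirubin and INR trigger restart without a 4- or 12-week wait, and the list guarantees only INR.

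**The case against.** The strongest reply is that full chemistry will be drawn anyway. ALT, AST, total bilirubin, albumin and creatine kinase all sit in the Table 12 Chemistry panel, and 8.4 covers unscheduled visits at any time and includes chemistry. A site ordering that panel gets direct bilirubin automatically. Footnote b refers to ALT elevations as 9.10.4 defines them, and 9.10.4 includes post-treatment follow-up. Figure 7 is not shown, and the laboratory manual is not among the documents; either might settle the matter.

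Much of this stands. A reader might infer a clean split, with mere inconsistency on treatment and a definite hole in follow-up. The documents do not support that: footnote b and 8.1 allow Table 9 to reach into follow-up, though its title limits it to the on-treatment period. What remains is that 8.4 names 9.10.4 as the minimum, so a site drawing only that list is compliant.

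The consequences are also limited. A flare found at a scheduled visit comes with direct bilirubin. The restart rule applies only to subjects who met the Treatment Stopping Criteria, so for others in Table 11 only visit frequency is at issue. The Investigator may add tests. The February 2023 termination (SAP 1 and 1.2) meant those criteria were not applied to subjects reaching Week 48 afterwards, which reduces the off-treatment group.

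**Conclusion.** The inconsistency is real on the current text. Three test lists and one table row make direct bilirubin conditional or omit it, while two safety rules use it unconditionally and Table 9 would have it measured. A site drawing only the 9.10.4 minimum could leave that limb unevaluated until the next scheduled chemistry: up to 4 weeks nominally, 38 days with follow-up windows, and sooner if total rises above ULN or chemistry is added.

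This rests on elevated meaning above ULN and on a direct ULN below half the total ULN. The assumed ULNs show only that it can happen. A reader might take the number of possible cells as a likelihood, but the documents give no ULNs and no frequencies.

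Nor is it a loss of protection. INR, albumin and symptoms remain in the decline rule; INR, clinical decompensation and Investigator discretion remain in the restart rule. No sample size, power or error rate is affected. It is a minor safety-wording point, worth correcting because the correction is cheap, and subject to Figure 7, which could not be checked.

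**What to change.** In the three 9.10.4 lists, replace total bilirubin and its reflex clause with total and direct bilirubin, and make the same change in the ALT Elevation Management row of Table 12. All thresholds stay as they are. This agrees with the Chemistry panel and the Table 9 Unscheduled Visit column, and closes the window for any pair of ULNs. It also fits the intent in the Amendment 1 rationale (Appendix 3), which favours fractionation whatever the total; that is cited as intent only. Figure 7 should be checked for the same wording.

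The cost is one added analyte per flare visit on blood already drawn, plus the protocol wording, with no extra visit or procedure. As the study has ended, the benefit is mainly for any reuse of this text.

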**LABORATORY VALUES\* CHEMISTRIES**

Parameter	Grade 1 Mild	Grade 2 Moderate	Grade 3 Severe	Grade 4 Potentially life-threatening
Acidosis	NA	pH $\geq$ 7.3 to < LLN	pH < 7.3 without life-threatening consequences	pH < 7.3 with life-threatening consequences
Albumin, Low (g/dL; g/L)	3.0 to < LLN 30 to < LLN	$\geq$ 2.0 to < 3.0 $\geq$ 20 to < 30	< 2.0 < 20	NA
Alkaline Phosphatase, High	1.25 to < 2.5 x ULN	2.5 to < 5.0 x ULN	5.0 to < 10.0 x ULN	$\geq$ 10.0 x ULN
Alkalosis	NA	pH > ULN to $\leq$ 7.5	pH > 7.5 without life-threatening consequences	pH > 7.5 with life-threatening consequences
ALT or SGPT, High Report only one	1.25 to < 2.5 x ULN	2.5 to < 5.0 x ULN	5.0 to < 10.0 x ULN	$\geq$ 10.0 x ULN
Amylase (Pancreatic) or Amylase (Total), High Report only one	1.1 to < 1.5 x ULN	1.5 to < 3.0 x ULN	3.0 to < 5.0 x ULN	$\geq$ 5.0 x ULN
AST or SGOT, High Report only one	1.25 to < 2.5 x ULN	2.5 to < 5.0 x ULN	5.0 to < 10.0 x ULN	$\geq$ 10.0 x ULN
Bicarbonate, Low (mEq/L; mmol/L)	16.0 to < LLN 16.0 to < LLN	11.0 to < 16.0 11.0 to < 16.0	8.0 to < 11.0 8.0 to < 11.0	< 8.0 < 8.0
Bilirubin Direct Bilirubin  , High > 28 days of age	NA	NA	> ULN with other signs and symptoms of hepatotoxicity	> ULN with life-threatening consequences (e.g., signs and symptoms of liver failure)
Total Bilirubin, High > 28 days of age	1.1 to < 1.6 x ULN	1.6 to < 2.6 x ULN	2.6 to < 5.0 x ULN	$\geq$ 5.0 x ULN
Calcium, High (mg/dL; mmol/L) $\geq$ 7 days of age	10.6 to < 11.5 2.65 to < 2.88	11.5 to < 12.5 2.88 to < 3.13	12.5 to < 13.5 3.13 to < 3.38	$\geq$ 13.5 $\geq$ 3.38
Calcium (Ionized), High (mg/dL; mmol/L)	> ULN to < 6.0 > ULN to < 1.5	6.0 to < 6.4 1.5 to < 1.6	6.4 to < 7.2 1.6 to < 1.8	$\geq$ 7.2 $\geq$ 1.8
Calcium, Low (mg/dL; mmol/L) $\geq$ 7 days of age	7.8 to < 8.4 1.95 to < 2.10	7.0 to < 7.8 1.75 to < 1.95	6.1 to < 7.0 1.53 to < 1.75	< 6.1 < 1.53
Calcium (Ionized), Low (mg/dL; mmol/L)	< LLN to 4.0 < LLN to 1.0	3.6 to < 4.0 0.9 to < 1.0	3.2 to < 3.6 0.8 to < 0.9	< 3.2 < 0.8

Parameter	Grade 1 Mild	Grade 2 Moderate	Grade 3 Severe	Grade 4 Potentially life-threatening
Cardiac Troponin I, High	NA	NA	NA	Levels consistent with myocardial infarction or unstable angina as defined by the local laboratory
Creatine Kinase, High	3 to < 6 x ULN	6 to < 10x ULN	10 to < 20 x ULN	≥ 20 x ULN

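### For a confirmed, clinically significant, drug-related ALT of at least 10x ULN without hepatic decline, Protocol 9.10.3 and 9.10.4 point to different actions, and no visible text says which governs

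*Combined protocol and SAP*

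**What the plan says.** **Grading (Protocol Appendix 1, Chemistries).** The row "ALT or SGPT, High" sets Grade 3 at 5.0 to below 10.0x ULN and Grade 4 at 10.0x ULN or more.

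**Grade 3 rule (9.10.2).** For a clinically significant laboratory abnormality, confirmed by repeat testing and considered related, "the study drug should be withheld until the toxicity returns to" Grade 2 or lower.

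**Grade 4 rule (9.10.3).** For a "clinically significant Grade 4 laboratory abnormality confirmed by repeat testing that is considered related to the study drug, the study drug should be permanently discontinued". The section's own laboratory exception is limited: "The study drug may be continued without dose interruption for a clinically nonsignificant Grade 4 laboratory abnormality". Its examples are creatine kinase and triglycerides. ALT is not mentioned.

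**ALT rule (9.10.4, branch without declining hepatic function).** The trigger is ALT above 2x Baseline or on-treatment nadir and at least 10x ULN. These subjects "should have the ALT findings confirmed within 3 days of receipt of the original results". One bullet then covers elevations caused by intercurrent illness. A separate, general bullet says: "Subjects with an ALT elevation without declining hepatic function and without contraindications may continue treatment with study drug under close observation". A later bullet directs discontinuation if ALT stays elevated for more than 4 weeks. The other branch, for declining hepatic function, directs discontinuation.

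**SAP 7.2.3.1** repeats the 10x ULN definition and the confirmation step and adds nothing on which rule governs.

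**The concern.** The general grade rules and the dedicated ALT section can apply to the same subject on the same day. One says the drug should stop for good. The other says the subject may stay on it while being watched.

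The choice carries into the analysis. The primary endpoint (Protocol 3.2.1) includes stopping treatment early because of adverse events. Protocol 9.7 says laboratory abnormalities are usually not recorded as adverse events, but must be when they lead to interruption or discontinuation. So the rule a site follows can decide both whether an adverse event is recorded and whether a discontinuation is counted. SAP 7.1.6 tabulates discontinuations separately for AB-729 and VBR, so those tables would move too.

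**Working it through.** No figure in the plan bears on this point, so the check compares thresholds and text, with two small pieces of arithmetic.

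**1. Do the two sections cover the same event?**

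- Lower bound of Grade 4 ALT (Appendix 1): 10.0x ULN.
- Trigger of the 9.10.4 branch: at least 10x ULN and above 2x Baseline or nadir.
- Screening limit (Protocol 5.3, criterion 11d): ALT of 5x ULN or more is exclusionary, so Screening ALT is below 5x ULN.

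The ULN thresholds are identical. That leaves the Baseline condition. Baseline is Day 1, whereas the limit applies at Screening, so an assumption is needed:

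- If Day 1 ALT is also below 5x ULN, then 2 x Baseline < 2 x 5 = 10x ULN. Any ALT of 10x ULN or more then exceeds 2x Baseline, and every on-treatment Grade 4 ALT meets the 9.10.4 trigger.
- If Day 1 ALT had risen to, say, 6x ULN, then 2 x 6 = 12x ULN. An ALT from 10x to 12x ULN would be Grade 4 without exceeding 2x Baseline, though it could still qualify through a lower on-treatment nadir.

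The overlap is therefore complete under the assumption and close to complete without it.

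**2. What does each section say for a confirmed, clinically significant, related case without hepatic decline?**

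| | 9.10.3 | 9.10.4 |
|---|---|---|
| ALT level | at least 10x ULN (Grade 4) | at least 10x ULN |
| Confirmation | repeat testing | repeat testing |
| Causality | must be related | not a condition |
| Clinical significance | required | not a condition |
| Instruction | should stop permanently | may continue; should stop if elevated for more than 4 weeks |

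**3. Does the text separate them?**

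- Causality does not. Intercurrent illness has its own bullet in 9.10.4, so the general continuation bullet is not confined to unrelated elevations.
- The exceptions in 9.10.3 do not. They cover clinically nonsignificant laboratory abnormalities and unrelated clinical events.
- The link between the sections does not. 9.10.4 introduces its guidance as additional, without saying that it replaces or yields to the grade rules. 9.10.3 does not refer to 9.10.4.
- The proviso about contraindications in 9.10.4 does not, because the term is undefined.

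**4. Weight of one subject (planned group sizes, Protocol Table 7).**

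- Group 1: 1/30 = 3.3 percentage points of the discontinuation proportion.
- Groups 2 and 3: 1/15 = 6.7 percentage points each.

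These are the weights of any single subject. They do not estimate how often the conflict arises.

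**The case against.** The strongest reply is that the sections can be read together. 9.10.4 permits continuation and does not order it, so a site that stops the drug under 9.10.3 breaches nothing. Because 9.10.4 is framed as additional, the grade rules could simply remain in force. Alternatively, the dedicated ALT section could be the specific rule that displaces the general one. A third reading is sequential: under Protocol 9.4 an event is related only if concurrent disease, other drugs or other events cannot explain it, and that judgement needs the work-up in 9.10.4, so 9.10.4 would apply during evaluation and 9.10.3 once relatedness is settled.

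Each reading is plausible, but they lead to different actions for the same subject and the text does not choose among them. Section 9.10 invites questions to the Medical Monitor and calls for consultation before interruption or discontinuation. That helps, but a site that keeps the subject on drug under 9.10.4 has no matching trigger to consult.

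Several limiting arguments stand:

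- The affected group is narrow. Symptoms of liver inflammation, an albumin fall of 0.5 g/dL or more, or INR above 1.5x Baseline, together with the ALT elevation, move a subject to the branch that directs stopping.
- Protocol 2.2.3.2 reports no Grade 4 laboratory abnormalities among 92 subjects through 24 weeks of Study 211.
- The abnormal-laboratory component of the primary endpoint captures the Grade 4 value whether or not the drug stops, and the analysis of that endpoint is descriptive.

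A reader might also infer that the protocol definitely treats a Grade 4 ALT more leniently than a Grade 3 ALT, since a related Grade 3 elevation is to be withheld under 9.10.2. That follows only if 9.10.4 overrides 9.10.3. If 9.10.3 governs, there is no inversion.

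**Conclusion.** The inconsistency is real for a defined case: ALT of at least 10x ULN that is confirmed, clinically significant and judged related, without declining hepatic function. For it, 9.10.3 says study drug should be permanently stopped, while 9.10.4 allows continuation and directs stopping only after more than 4 weeks of elevation. Sites could act differently within the protocol, and the adverse-event discontinuation component of the primary endpoint could differ as a result. If 9.10.4 overrides, a related Grade 3 ALT would also be handled more strictly than a related Grade 4 ALT.

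The size is one subject's weight per affected case, 3.3 points in Group 1 or 6.7 points in Group 2 or 3 at planned sizes. The number of cases is not given.

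It would go too far to say that every Grade 4 ALT triggers two opposed commands. 9.10.3 is confined to clinically significant, related abnormalities and is worded as should; 9.10.4 is worded as may. Nor can one say that precedence is stated nowhere, because Figure 7 was not visible. The conclusion rests on the visible text and, for complete overlap, on Day 1 ALT being below 5x ULN.

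**What to change.** Reconcile Protocol 9.10.2, 9.10.3, 9.10.4 and Figure 7, with one explicit statement of which section governs related ALT elevations of Grade 3 and of Grade 4. The choice of rule is for the sponsor; this review takes no position on it. The cost is a sentence or two in a clarification or amendment, or in any later protocol that reuses this text.

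SAP section 1 says the study was terminated after every active subject completed the 48-week treatment period, so new wording cannot change on-treatment decisions already taken. For this trial, the synoptic CSR should state which section was applied and list every confirmed, related Grade 3 or Grade 4 ALT elevation with the action taken on each study drug. SAP 7.1.3 takes relatedness from the adverse event form, and a subject kept on drug may have no such form under Protocol 9.7. The listing should therefore start from all confirmed Grade 3 and 4 ALT values and show where no causality assessment was recorded. It is one listing, built from laboratory, adverse event and dosing data that the SAP already plans to list.
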